8.1.1. Adverse Events Leading to Withdrawal

A summary of incidence rates (frequencies and percentages) of TEAEs leading to discontinuation of study drug will be summarized by period (Visit 2 [Baseline] and Visit 14 [End of Treatment/Follow-Up]), and by SOC and preferred term for the Safety population. No inferential statistical tests will be performed.

A data listing of AEs leading to discontinuation of study drug will also be provided, displaying details of the event(s) captured on the eCRF.

8.1.2. Deaths and Serious Adverse Events

Any deaths that occur during the study will be listed.

Serious AEs will be listed. Serious TEAEs and serious TEAEs related to IP will be tabulated by SOC and preferred term and presented by period (post-consent and prior to IP administration at Visit 2 [Baseline] and post-Visit 2 through Visit 15 [End of Treatment/Follow-up]).

8.2. Clinical Laboratory Evaluations

Descriptive summaries of observed values and change values will be presented for continuous hematology, chemistry, and urinalysis results for overall subjects at each study Visit. Ninety-five percent CIs for the change and percent change will be included. Categorical urinalysis results will be summarized using frequencies by overall subjects and by study Visit.

The number of subjects with clinical laboratory values categorized as below, within, or above normal ranges will be tabulated showing change from baseline (shift tables) for each clinical laboratory analyte by overall subjects and by study Visit.

Laboratory values that are outside the normal range will also be flagged in the data listings and presented with the corresponding normal ranges. Any out-of-range values that are identified by the investigator as being clinically significant will also be shown in a data listing.

For women only, pregnancy status will be determined by evaluation of urine pregnancy test.

Data on pregnancy status will be listed by subjects. Subjects who are pregnant are excluded from the study. Subjects who become pregnant during the study will be discontinued.

8.3. Vital Signs

Descriptive summaries of observed values and changes from baseline will be calculated for systolic blood pressure (mmHg), diastolic blood pressure (mmHg), heart rate (beats/min), respiratory rate (breaths/min), and temperature (°C) by overall subjects and by study Visit.

8.4. Electrocardiograms

The number and percentage of subjects with normal and abnormal 12-lead ECG findings will be summarized for overall subjects at each study Visit. Abnormal results will be grouped as clinically significant and not clinically significant.

Descriptive summaries for the observed results and change from baseline will be presented for 12-lead ECG measures of PR interval (msec), QRS interval (msec), and heart rate for overall subjects at each study Visit. If triplicate reads are taken, the mean of the reads will serve as the observed value at the specific Visit.

A comparison of QT and QTcF results will be presented. Summary statistics for baseline values at post-consent and prior to IP administration at Visit 2 [Baseline] and post-Visit 2 through final Visit/follow-up phone call will be displayed by overall subjects for QT interval (msec) and QT interval corrected for heart rate using Fridericia's formula (QTcF) (msec).

$$\text{Fridericia's Correction} \quad (QT_{cf}) \quad QT_{cf} = \frac{QT_{\text{msec}}}{\sqrt[3]{RR}}$$

8.5. Concomitant Medication

Concomitant medications will be summarized descriptively using counts and percentages for the Safety population. Medications will be summarized overall, by the number and percentage of subjects taking each medication and classified by ATC class and preferred term. Data will also be presented in a by-subject listing, which will include ATC Level 2 classification, preferred term and verbatim name.

Prior medications will be presented separately from concomitant medications. All medications taken in the month prior to Visit 1 (Screening) or in the time interval between Visit 1 (Screening) and Visit 2 (Baseline) will be considered prior medications, whether or not they were stopped before Visit 2 (Baseline). Any medications continuing or starting after Visit 2 (Baseline) will be considered concomitant. If a medication starts before Visit 2 (Baseline) and continues after Visit 2 (Baseline) it will be considered both prior and concomitant.

Medications will be coded using WHO-DD, as described in Section **Error! Reference source not found.**

8.6. Columbia-Suicide Severity Rating Scale (C-SSRS)

The C-SSRS is a semi-structured interview that captures the occurrence, severity, and frequency of suicide-related thoughts and behaviors during the assessment period. The interview includes definitions and suggested questions to solicit the type of information needed to determine if a suicide-related thought or behavior has occurred. The C-SSRS has a “baseline” version, which will be completed at Visit 1 (Screening), and a “since last Visit” version that will be completed at all subsequent Visits.

There are a maximum of 19 items to be completed: 7 that are required, 10 potential additional items if there is a positive response to a required item, and 2 items for suicide/suicide behavior present during the interview. The C-SSRS uses dichotomous scales (i.e., yes or no), Likert scales, and text or narrative to further describe the thoughts or behaviors.

The number and percentage of subjects reporting “Yes” for any of the 5 suicidal ideation questions (Categories 1 to 5) or any of the 5 suicidal behavior questions (Categories 6 to 10) will be displayed for overall subjects, along with the number and percentage reporting suicidal ideation OR behavior (Categories 1 to 10). Treatment-emergent suicidal ideation and behavior (an increase in maximum score during treatment) will also be presented.

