#### 8.2.2 Exclusion Criteria

To be considered eligible for entry into the study, a subject must not meet any of the following exclusion criteria at study entry.

1. Any history of bipolar disorder (I or II), schizophrenia, schizoaffective disorder, psychosis, anorexia or bulimia, premenstrual dysphoric disorder, autism-spectrum disorder, obsessive-compulsive disorder, or treatment-refractory major depressive disorder.

Any other current Axis I disorder, other than SAD, which is the primary focus of treatment. Note that subjects with concurrent Generalized Anxiety Disorder are eligible for the study provided that Generalized Anxiety Disorder is not the primary diagnosis.

2. In the opinion of the Investigator, the subject has a significant risk for suicidal behavior during the course of their participation in the study, or
  - a. At Screening (for subjects who attend Visit 1): the subject scores “yes” on items 4 or 5 in the Suicidal Ideation section of the Columbia-Suicide Severity Rating Scale (C-SSRS) with reference to a 6-month period prior to screening; or
  - b. At Screening (for subjects who attend Visit 1): the subject has had 1 or more suicidal attempts with reference to a 2-year period prior to screening; or
  - c. At Baseline (Visit 2): the subject scores “yes” on items 4 or 5 in the Suicidal Ideation section of the C-SSRS with reference to last visit; or
  - d. The subject is considered to be an imminent danger to themselves or others.
3. Subjects using the following psychotropic medications at enrollment or within 30 days before study entry: antidepressants (including monoamine oxidase [MAO] inhibitors), anxiolytics, stimulants, anticonvulsants, mood stabilizers, antipsychotic medications, gabapentin, pregabalin, opioids, naltrexone, esketamine, and ketamine. Eszopiclone, ramelteon, melatonin, zaleplon, zolpidem, or anti-histamines prescribed for insomnia are allowed.
4. Use of benzodiazepines or unapproved treatments such as beta blockers, within 30 days before study entry and during the study. Use of beta blockers for treatment of hypertension or cardiac conditions is allowed. Subjects who have been taking benzodiazepines daily for 1 month or longer at the time of Visit 1 are not eligible to participate.
5. Use of any over-the-counter product or herbal preparation for treatment of the symptoms of anxiety or social anxiety within 30 days before study entry; concomitant use is prohibited during the study.

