### **10.2.2 Treatment Period**

#### **10.2.2.1 Visit 2 (Baseline)**

Subjects entering the study within 14 days of their antecedent PH94B SAD study will enter this study at Visit 2. These subjects will sign an ICF for the present study at this visit and complete all Visit 2 assessments as noted in the schedule of events (Table 2-1) and detailed in this section.

All subjects will complete the following Visit 2 assessments:

- Obtain urine sample for urine drug screen: Instant Exam to be performed on site, with results thoroughly documented in the source; urine samples will be sent to the central laboratory for confirmation as needed if on-site urine drug screen is positive. If the central laboratory urine drug screen result is positive [REDACTED]

[REDACTED], the subject may have to be excluded from the study; the Medical Monitor should be consulted on these cases

- For females of childbearing potential, obtain urine sample and complete on-site urine pregnancy test
- Record concomitant medication use
- Perform physical examination, including body weight (pounds). The physical examination includes a review of the nasal passages
- Measure vital signs after the subject has rested for 5 minutes: seated systolic and diastolic blood pressure, heart rate, respiratory rate, and body temperature (°F)
- Obtain 12-lead ECG in supine position after the subject has rested for 5 minutes
- Obtain blood and urine samples for evaluation by the central clinical laboratory, including hematology, chemistry, thyroid functioning, and urinalysis
- Review all inclusion and exclusion criteria

For subjects meeting all study inclusion criteria and no study exclusion criteria, the following Visit 2 procedures will be performed:

- Administer the LSAS
- Administer the HAM-D17
- [REDACTED]
- Administer the C-SSRS (Since Last Visit)
- Complete the CGI-S with a recall period of 1 week (by the trained clinician)
- Train subjects on the use, dosing, and storage of IP. The subject will be given instructions on:
  - how to position the actuator nozzle in the nasal passages and self-administer IP
  - the number of sprays per nostril per dose (1 per nostril)
  - how to store the nasal spray
  - Treatment with PH94B should be self-administered approximately 15 minutes prior to or during an anxiety-provoking social situation or event. [REDACTED]  
[REDACTED], with no more than 4 administrations per day. Treatment does not need to be administered every day.

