b Pregnancy tests will only be given to female subjects of childbearing potential and not post-menopausal females.

c 12-Lead electrocardiograms will be administered to subjects at the Screening and Baseline Visits and then every month during the study.

d Physical examination will include measurement of weight and an examination of the nasal passages. Height will be measured at Screening and at Visit 14.

e If total anosmia is suspected during review of the nasal passages at Visit 1, the Quick Olfactory Test (QOT) is to be administered.

f Note: Long-term C-SSRS will be administered at screening. All other C-SSRS will be "Since Last Visit".
Note: If central laboratory urine drug screen testing is positive for a subject, then the participation of the subject in the study may have to be discontinued. The Medical Monitor should be consulted on these cases. An unscheduled repeat urine drug screen may be obtained to investigate whether drug use is continuing.

4. Statistical Analysis and Reporting

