6.1. Statistical Definitions and Algorithms

6.1.1. Baseline

The last observation recorded before the first dose of PH94B will be used as the baseline observation for all calculations of change from baseline.

Table 1: Baseline Definitions

Parameter	Baseline
Safety Variables (clinical laboratory assessments, vital signs, ECGs, physical examinations)	The last non-missing assessment before the first dose of study drug given at Visit 2 (Baseline).
C-SSRS Scores	Scores on the Baseline version of the C-SSRS given at Visit 1 (Screening).
LSAS total score, HAM-D total score, [REDACTED]	Total score at Visit 2 (Baseline).

Abbreviations: CGI-I = Clinical Global Impression of Improvement; ECG = electrocardiogram; C-SSRS = Columbia-Suicide Severity Rating Scale; [REDACTED] HAM-D = Hamilton Depression Scale; LSAS = Liebowitz Social Anxiety Scale

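### SAP 8.6 counts suicidality as treatment-emergent on a rise in maximum C-SSRS score but names no comparator; under the SAP's C-SSRS baseline row, on-drug events no worse than the recorded history do not get that label

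*SAP*

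**What the plan says.** SAP 8.6 gives the rule: "Treatment-emergent suicidal ideation and behavior (an increase in maximum score during treatment) will also be presented". The same section numbers ideation as Categories 1 to 5 and behaviour as Categories 6 to 10. It also plans "the number and percentage reporting suicidal ideation OR behavior (Categories 1 to 10"), with no baseline condition. SAP 12.3 lists a C-SSRS table by study visit (Table 14.3.6.5).

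SAP 6.1.1 holds two baseline rules that bear on this. Its opening sentence reads: "The last observation recorded before the first dose of PH94B will be used as the baseline observation for all calculations of change from baseline". The C-SSRS row of the table beneath it reads: "Scores on the Baseline version of the C-SSRS given at Visit 1 (Screening"). On recall, the notes to the SAP 3.5 schedule state that "Long-term C-SSRS will be administered at screening", and the protocol's schedule carries the same note. Every later rating covers only the time since the previous visit. That includes Visit 2, where protocol 10.2.2.1 lists "Administer the C-SSRS (Since Last Visit").

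Protocol 8.2.2, criterion 2, limits past suicidality by look-back. Ideation items 4 or 5 exclude "with reference to a 6-month period prior to screening" (2a). Attempts exclude if "the subject has had 1 or more suicidal attempts with reference to a 2-year period prior to screening" (2b). A yes on items 4 or 5 at Visit 2 also excludes (2c), as do investigator judgement and imminent danger.

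**The concern.** A treatment-emergent count is normally read as separating what appears or worsens on drug from what was there just before. If the comparator is a long-recall form, the worst episode in a subject's recorded history is set against ratings that each cover about a month. Subjects with a serious but old history are then the hardest to flag.

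Suicidality is named in the primary objective (protocol 6.1, SAP 2.1.1), and change in C-SSRS is a listed safety endpoint. The study has no comparator arm (protocol 7.2), no data safety monitoring board (protocol 12) and, in the SAP, no interim analysis (SAP 4.2). The wording of this one derivation therefore carries some weight, and two programmers following SAP 6.1.1 could produce different counts.

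**Working it through.** **Which comparator.** SAP 8.6 is silent. The C-SSRS row of the 6.1.1 table is specific to this scale and would usually be taken to override the general sentence. It gives the Visit 1 long-term form. The general sentence gives the last rating before first dose, which is the Visit 2 rating.

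**Does eligibility make the two agree?** No. Criteria 2a and 2b leave in subjects with items 4 or 5 more than 6 months before screening, with attempts more than 2 years before, or with items 1 to 3 at any time. Criterion 2c does bound the Visit 2 rating: an eligible subject has at most item 3 there. Against Visit 2, new on-drug ideation at item 4 or 5 is therefore always an increase. Against the long-term form it need not be.

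**The rule applied.** Label as emergent if and only if the on-drug maximum exceeds the comparator. Constructed cases, on a 0-to-10 scale:

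| Long-term maximum | Visit 2 maximum | On-drug maximum | Emergent, C-SSRS row | Emergent, Visit 2 |
|---|---|---|---|---|
| 0 | 0 | 3 | yes | yes |
| 3 | 0 | 2 | no | yes |
| 3 | 0 | 3 | no | yes |
| 3 | 0 | 4 | yes | yes |
| 5 | 0 | 4 | no | yes |
| 8 | 0 | 5 | no | yes |
| 8 | 0 | 8 | no | yes |
| 0 | 2 | 2 | yes | no |

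The last row shows the effect is mainly, not strictly, downward: ideation that first appears between Visits 1 and 2 and continues on drug is labelled emergent under the C-SSRS row. The row (8, 0, 5) depends on one ladder across ideation and behaviour. If maxima are taken by domain, it is labelled unless the recorded historical ideation was already 5. The rows (5, 0, 4) and (8, 0, 8) are unlabelled either way.

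**Subjects entering at Visit 2.** Protocol 7.1 sends subjects within 14 days of their antecedent study straight to Visit 2. The screening data to be transcribed for them (protocol 10) are demographics, MINI, medical and psychiatric history, and the diagnostic checklist. The C-SSRS is not among them, so the C-SSRS row gives them no baseline.

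**Size, as illustration.** The plan has no figure to reproduce and no history rate. Assume:
- a share h = 20% to 50% with any positive long-term item;
- on-drug positives r = 1 to 5 times as frequent with history as without;
- historical maximum over items 1, 2, 3, 4, 5 and attempt with probabilities 0.30, 0.25, 0.10, 0.10, 0.10, 0.15;
- on-drug maximum over the same set with 0.45, 0.25, 0.10, 0.10, 0.05, 0.05, independent of history severity.

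The chance m that the on-drug maximum does not exceed history, given history, is

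0.30×0.45 + 0.25×0.70 + 0.10×0.80 + 0.10×0.90 + 0.10×0.95 + 0.15×1 = 0.725.

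The share of on-drug positives left unlabelled is m × h×r / (h×r + 1 − h):
- h = 20%, r = 1: 0.725 × 0.20/1.00 = 15%
- h = 35%, r = 3: 0.725 × 1.05/1.70 = 45%
- h = 50%, r = 5: 0.725 × 2.50/3.00 = 60%

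This uses the combined ladder. Taking maxima by domain, and supposing subjects with a past attempt have no recorded ideation, the last term of m becomes 0.15×0.05 and m = 0.5825. The range is then 0.5825 × 0.20 = 12% to 0.5825 × 0.833 = 49%.

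**The case against.** The strongest reply is that nothing is lost. The any-positive counts in SAP 8.6 carry no baseline condition, so every constructed on-drug case above appears in them, beside the treatment-emergent figure. Protocol 10.2.2.1 also treats recurring adverse events as new ones, and the HAM-D suicide item is rated monthly. This stands. A reader might infer that on-drug suicidality in subjects with a history goes unreported; the documents do not support that. What the any-positive display cannot do is separate new or recurrent suicidality from suicidality already present before dosing, which is the purpose of the treatment-emergent count.

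Second, the general sentence in SAP 6.1.1 would lead to Visit 2, and under it the problem disappears. That is a fair reading, but the C-SSRS row contradicts it, and the SAP does not say which governs.

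Third, a reader might infer that a past attempt prevents any ideation score from being flagged. That needs a single ladder from 1 to 10. SAP 8.6 describes the two domains separately and does not say how the maximum is formed, so the inference is not established.

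Fourth, comparing against history is a choice a sponsor may make deliberately, and the wording speaks only of an increase. True, but the plan does not state that choice, and it cannot be applied to subjects with no screening form.

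**Conclusion.** The point holds as a defect of definition. The comparator is unstated in SAP 8.6, and SAP 6.1.1 supports two answers that give different counts. Under the scale-specific answer, a recurrence at or below the recorded historical maximum cannot be labelled treatment-emergent, and subjects without a Visit 1 form have no comparator. This follows from the text and needs no assumed rate. 'Recorded history' means whatever recall the long-term form covers, which neither document states.

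The size is unknown. The 15% to 60% range rests wholly on assumed rates and, at those values, on a combined ladder. It should not be turned into a number of subjects out of the planned 600: the masking applies only to those with a Visit 1 form, and the documents do not give their share. Some of the unlabelled positives would be continuations of a pre-drug state and would rightly stay unlabelled. The change is worth making because it is cheap and concerns a variable in the primary objective, not because a large undercount has been shown.

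**What to change.** In SAP 6.1.1 and 8.6:

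- Name the Visit 2 rating (since last visit) as the comparator for treatment-emergence, for all subjects, and align the C-SSRS row with it.
- Add the recent 6-month ideation rating from Visit 1 only where it was recorded. Criterion 2a needs only items 4 or 5 over that window and excludes subjects who have them, so for eligible subjects it could add only items 1 to 3. No section shows that these are stored.
- Take the maximum separately for ideation (Categories 1 to 5) and behaviour (Categories 6 to 10), and say so.
- Keep the comparison with the long-term form as a second display, stating its recall period, and show treatment-emergent counts with and without prior history. Say how history is classified for subjects with no Visit 1 form.

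The cost is SAP wording and one derivation; the Visit 2 rating is already scheduled for every subject. The downside is that the reported treatment-emergent count may rise. Because the Visit 2 recall is short (7 to 35 days after a screening visit), it may also include some fluctuating pre-existing ideation. For subjects entering at Visit 2, the SAP should also say which earlier visit the rating refers back to, since the documents do not.

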8.7. Penn Physician Withdrawal Checklist

The PWC-20 consists of 20 questions related to withdrawal from benzodiazepines or other anti-anxiety compounds. The symptoms measured are based on those that are potentially related to anxiolytic withdrawal: gastrointestinal, mood, sleep, motor, somatic, perception, and cognition. The questions will cover any symptoms that might occur during the week following discontinuation of PH94B.

Summaries of PWC-20 total scores and frequency and percentage of subjects with withdrawal symptoms will be presented overall for only those subjects who completed both Visit 14 and Visit 15. Descriptive statistics for total scores and frequencies of withdrawal symptoms will be presented by Visit 1 and Visit 15.

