#### 13.1.1 Analysis Populations

A single analysis population is planned for this study:

- Safety population: All subjects who receive IP.

All analyses will be performed using the Safety population.

Primary and exploratory endpoints may be summarized by subgroups of interest including age, sex, concomitant medications, and SAD severity. Analysis of subgroups not pre-defined in the final SAP will be labeled as such in the clinical study report (CSR).

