#### **13.1.4.5 Penn Physician Withdrawal Checklist**

Descriptive summaries (mean, SD, median, minimum, and maximum) will be presented for scores from the PWC-20 checklist, completed at Visits 14 and 15.

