2.2. Study Endpoints

2.2.1. Safety Endpoints

The safety endpoints of this study include the following:

- Incidence and severity of AEs, AEs leading to discontinuation, and SAEs
- Changes in vital signs results
- Changes in clinical laboratory evaluation (hematology, chemistry, and urinalysis) results
- Changes in 12-lead ECG results
- Changes in physical examination findings
- Changes in HAM-D17 scores
- Changes in C-SSRS scores
- PWC-20 scores after termination of PH94B

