6.1.4. Handling of Dropouts or Missing Data

Only observed data will be included in the final report.

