6.1.8. Data Adjustments/Handling/Conventions

All collected data will be presented in listings. Data not subject to analysis according to this plan will not appear in any tables or graphs but will be included only in the data listings.

Medical history and AEs (all types) will be coded using the most recent version of the Medical Dictionary for Regulatory Activities (MedDRA), version 25.1. Prior and concomitant medications will be coded using the World Health Organization Drug Dictionary (WHO-DD) Anatomical Therapeutic Chemical (ATC) classes and preferred terms, version WHODrug B3 Global Sep 2021.

If partial dates occur, the convention for replacing missing dates for the purpose of statistical analysis is as follows: if just day is missing then the day assigned is the first day of the month or the date of first dose (if in the same month), whichever is later; if just month is missing then the month assigned is the month of the first dose, unless that results in a date before the first dose in

which case the month after the first dose is used; and if both month and day are missing then the month assigned is the month of the first dose and the day assigned is either the first day of the month or the first dose date, whichever is later.

If partial times occur, the convention is as follows: if the missing time occurs on the day of the first dose and both the hour and minute are missing then the time assigned is the time of the first dose, otherwise if both the hour and minute are missing and the date is not the date of first dose the time assigned is 12:00; if the date is the same as the date of the first dose and only hour is missing the hour assigned is 12 or the hour of first dose, whichever is later, and if the date is the same as the date of first dose and only the minute is missing the minute assigned is 30 or the minute of first dose, whichever is later. Otherwise the hour assigned is 12 if the hour is missing and the date is not the same as the date of first dose and the minute assigned is 30 is the the date is not the same as the date of first dose.

These conventions will be applied only to AE and medication onset dates and times with the following precaution: if the missing date and time reflect the date and time of onset of an AE, the modified date and time will be constructed to match the first documented date/time post drug administration while preserving the order in which the AE/medication was reported in the eCRF.

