14.5 Other Data Summary Tables		
Table 14.5.1	Safety	Hamilton Depression Scale (HAM-D): Observed Results and Change from Baseline by Study Visit
Table 14.5.3	Safety	Summary of Physician Withdrawal Checklist (PWC-20)

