16.2 Subject Data Listings		
Listing 16.2.9.3	All Enrolled Subjects	Physical Examination Measurements
Listing 16.2.9.4	All Enrolled Subjects	Quick Olfactory Test (QOT)
Listing 16.2.9.5	All Enrolled Subjects	Prior and Concomitant Medications
Listing 16.2.9.6	All Enrolled Subjects	Columbia Suicide Severity Rating Scale (C-SSRS) Screening
Listing 16.2.9.7	All Enrolled Subjects	Hamilton Depression Rating Scale (HAM-D)
[REDACTED]	[REDACTED]	[REDACTED]
Listing 16.2.9.9	Subects with Visit 14 and Visit 15	Physician Withdrawal Checklist (PWC-20)
[REDACTED]	[REDACTED]	[REDACTED]

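### SAP 8.7 and Listing 16.2.9.9 confine PWC-20 reporting to subjects with both Visit 14 and Visit 15, an undeclared restriction that conflicts with the protocol and with other parts of the SAP

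*SAP*

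**What the plan says.** Withdrawal symptoms are part of the primary objective in Protocol 6.1, and SAP 2.2.1 lists "PWC-20 scores after termination of PH94B" among the safety endpoints. Protocol Table 2-1 schedules the PWC-20 at Visit 14/ET and at Visit 15 only.

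On the analysis, the protocol plans descriptive summaries of "scores from the PWC-20 checklist, completed at Visits 14 and 15" (13.1.4.5) and states that "All analyses will be performed using the Safety population" (13.1.1). Neither section requires attendance at both visits.

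The SAP is not consistent:

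- Section 8.7 limits the summaries to "only those subjects who completed both Visit 14 and Visit 15".
- The listing plan in 12.5 gives the population of Listing 16.2.9.9 as "Subects with Visit 14 and Visit 15" (spelling as in the SAP).
- Section 6.1.8 says "All collected data will be presented in listings".
- Section 6.1.4 says "Only observed data will be included in the final report" and adds no complete-pair rule.
- The table plan in 12.4 gives the population of Table 14.5.3, the only PWC-20 table, as Safety, with no visit condition.
- Section 10, on changes from the planned analysis, does not mention the restriction.

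**The concern.** The paired-attendance rule selects subjects on something that happens around or after the end of treatment: whether they came to both the termination visit and the follow-up about two weeks later. A subject who stops early, attends the termination visit and never returns has an observed PWC-20 score that 8.7 and Listing 16.2.9.9 both leave out. So does a subject seen only at Visit 15, and so does a 12-month completer who misses Visit 15.

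Such subjects are foreseeable. Protocol 8.3 asks sites to make every attempt to obtain the early-termination assessments. Protocol 14.6.1 says that, if the study is terminated, sites may be asked to complete the Visit 14/ET assessments, and it does not mention Visit 15.

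At stake is a descriptive safety endpoint that belongs to the primary objective. If non-return is related to how people feel after stopping, the reported symptom frequency could be too low, and the listing would not let a reader see the omitted scores.

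**Working it through.** **1. Text comparison.** The plan states no PWC-20 sample size, rate or attendance figure, so there is nothing to reproduce. The first check is which scores each section would report.

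| Source | Subjects whose PWC-20 is reported |
|---|---|
| Protocol 13.1.1 and 13.1.4.5 | Safety population, at Visits 14 and 15 |
| SAP 8.7 (summary) | Both visits only |
| SAP 12.4, Table 14.5.3 | Safety, no visit condition |
| SAP 12.5, Listing 16.2.9.9 | Both visits only |
| SAP 6.1.8 (all listings) | Everyone with data |

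The summary and the listing each have one instruction that keeps one-visit subjects and one that drops them. The listing plan writes the restriction in its population column and the table plan does not, so a programmer cannot tell which was intended for the table. No other visible listing is restricted by visit attendance. For the exploratory endpoints, SAP 7.5 uses everyone who completed the visit in question, without pairing.

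**2. What a one-visit score measures.** Under Protocol 7.1 an early terminator attends the ET visit, labelled Visit 14, promptly after stopping, and Visit 15 about two weeks later. That ET score may therefore be post-discontinuation. Under Protocol 10.2.3, if the decision to stop is taken at a scheduled visit, the ET assessments are done there, so the score can fall at the moment of stopping. A scheduled Visit 14 score is taken at the end of treatment. These scores differ in meaning and should not be merged under one visit label.

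**3. Illustration on assumed inputs.** N = 600 is the protocol's maximum. The share f with exactly one of the two visits is assumed, everyone is taken to have at least one score, and which visit it came from is ignored.

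- Subjects dropped = 600 × f; retained n = 600 × (1 − f).
- One-sided 95% upper bound for a symptom seen in nobody = 1 − 0.05^(1/n). With n = 600 it is 0.50%.
- Rate in all observed subjects = (1 − f) × p_both + f × p_one. The restricted table shows p_both, taken as 5%.

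| f | Dropped | n | Zero-event bound | All-observed rate, p_one = 5% | p_one = 10% | p_one = 20% |
|---|---|---|---|---|---|---|
| 5% | 30 | 570 | 0.52% | 5.0% | 5.25% | 5.75% |
| 10% | 60 | 540 | 0.55% | 5.0% | 5.5% | 6.5% |
| 20% | 120 | 480 | 0.62% | 5.0% | 6.0% | 8.0% |
| 30% | 180 | 420 | 0.71% | 5.0% | 6.5% | 9.5% |
| 40% | 240 | 360 | 0.83% | 5.0% | 7.0% | 11.0% |

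Example: f = 20%, p_one = 20% gives 0.8 × 5% + 0.2 × 20% = 8.0%, against 5.0% in the restricted table. With equal rates there is no bias, only fewer subjects.

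**The case against.** The best defence is that pairing is a reasonable choice for this instrument. There is no pre-treatment PWC-20, so an isolated score cannot separate withdrawal from the anxiety, mood or sleep symptoms that these subjects may already have. Using the same people at both visits keeps the comparison like for like. This stands as a reason to keep a paired panel. It does not justify making that the only output: 8.7 asks for totals and frequencies, which need no pairing, and the SAP gives no rationale for the limit.

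Three stronger readings are tempting, and the documents do not support them.

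- A reader might infer that one-visit scores are certain to appear nowhere. SAP 6.1.8 and the Safety label on Table 14.5.3 point the other way, so this is an unresolved conflict. Symptoms recorded as adverse events at these visits also reach the report through the adverse-event outputs, though the PWC-20 score itself does not.
- A reader might treat every early-termination score as off-drug. Protocol 10.2.3 shows otherwise, no minimum interval after stopping is set, and as-needed dosing blurs the boundary further. The instrument is meant to cover the week after discontinuation, and some ET scores may cover little of it.
- A reader might conclude that the endpoint is biased toward mild symptoms. That is plausible, but no document figure shows the direction. Early terminators who attend both visits are kept.

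It is also fair to say that the PWC-20 is one of eight listed safety endpoints and is reported without formal testing.

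**Conclusion.** The concern holds as a conflict that needs resolving. SAP 8.7 and Listing 16.2.9.9 restrict PWC-20 reporting in a way that the protocol does not, that disagrees with SAP 6.1.8 and with the population given for Table 14.5.3, and that section 10 does not declare. Following 8.7 and the listing plan literally would leave observed scores on a primary-objective endpoint out of that summary and listing, selected on attendance.

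The size is unknown. The range of 30 to 240 subjects, and the gap between 5.0% and as much as 11.0%, rest entirely on assumed attendance and symptom rates. Understatement of withdrawal symptoms is possible if non-attendance is related to symptoms; otherwise the cost is information only. The change is worth making because it is cheap and removes the need to guess which case applies.

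**What to change.** 1. Reword SAP 8.7 to summarise all observed PWC-20 totals and symptom frequencies by visit in the Safety population, with scheduled Visit 14 and early termination in separate columns and n shown for each.
2. Keep the subjects with both visits as a supplementary paired panel for the Visit 14 to Visit 15 comparison.
3. Change the population of Listing 16.2.9.9 so that every PWC-20 record is listed, in line with SAP 6.1.8. Make the Table 14.5.3 entry agree with the reworded 8.7.
4. In the same paragraph of 8.7, correct the sentence that presents results at Visit 1 and Visit 15: the PWC-20 is scheduled only at Visit 14/ET and Visit 15.
5. If the paired set is retained as the main analysis, declare it in SAP section 10 with the reason.

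The cost is SAP wording and one extra table panel. No additional data are needed.
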